ATTACHMENT 2: ANTICIPATED EVENTS

An anticipated event is an adverse event (serious or non-serious) that commonly occurs as a consequence of the underlying disease or condition under investigation (disease related) or background regimen.

For the purposes of this study the following events will be considered anticipated events:

- Exacerbations of rheumatoid arthritis (RA)
- Worsening joint pain or swelling due to RA
- Synovitis

Reporting of Anticipated Events

These events will be captured on the CRF and in the database, and will be reported to the sponsor as described in Section 12.3.1, All Adverse Events. Any event that meets serious adverse event criteria will be reported to the sponsor within the appropriate timeline as described in Section 12.3.2, Serious Adverse Events. These anticipated events are exempt from expedited reporting as individual single cases to Health Authorities. However, if based on an aggregate review, it is determined that an anticipated event is possibly related to study drug, the sponsor will report these events in an expedited manner.

Anticipated Event Review Committee (ARC)

An Anticipated Event Review Committee (ARC) will be established to perform reviews of pre-specified anticipated events at an aggregate level. The ARC is a safety committee within the sponsor's organization that is independent of the sponsor's study team. The ARC will meet to aid in the recommendation to the sponsor's study team as to whether there is a reasonable possibility that an anticipated event is related to the study drug.

Statistical Analysis

Details of statistical analysis of anticipated events, including the frequency of review and threshold to trigger an aggregate analysis of anticipated events will be provided in a separate Anticipated Events Safety Monitoring Plan (ASMP).

APPENDIX A QUANTIFERON®-TB GOLD TESTING

The QuantiFERON-TB Gold test is one of the interferon- γ (IFN- γ) based blood assays for TB screening (Cellestis, 2009). It utilizes the recently identified *M. tuberculosis*-specific antigens ESAT-6 and CFP-10 in the standard format, as well as TB7.7 (p4) in the In-Tube format, to detect in vitro cell-mediated immune responses in infected individuals. The QuantiFERON-TB Gold assay measures the amount of IFN-g produced by sensitized T-cells when stimulated with the synthetic *M. tuberculosis*-specific antigens. In *M. tuberculosis*-infected persons, sensitized T lymphocytes will secrete IFN- γ in response to stimulation with the *M. tuberculosis*-specific antigens and, thus, the QuantiFERON-TB Gold test should be positive. Because the antigens used in the test are specific to *M. tuberculosis* and not found in BCG, the test is not confounded by BCG vaccination, unlike the tuberculin skin test. However, there is some cross-reactivity with the 3 Mycobacterium species, *M. kansasii*, *M. marinum*, and *M. szulgai*. Thus, a positive test could be the result of infection with one of these 3 species of Mycobacterium, in the absence of *M. tuberculosis* infection.

In a study of the QuantiFERON-TB Gold test (standard format) in subjects with active TB, sensitivity has been shown to be approximately 89% (Mori et al, 2004). Specificity of the test in healthy BCG-vaccinated individuals has been demonstrated to be more than 98%. In contrast, the sensitivity and specificity of the tuberculin skin test was noted to be only about 66% and 35% in a study of Japanese patients with active TB and healthy BCG-vaccinated young adults, respectively. However, sensitivity and specificity of the tuberculin skin test depend on the population being studied, and the tuberculin skin test performs best in healthy young adults who have not been BCG-vaccinated.

Data from a limited number of published studies examining the performance of the QuantiFERON-TB Gold assay in immunosuppressed populations suggest that the sensitivity of the QuantiFERON-TB Gold test is better than the tuberculin skin test even in immunosuppressed patients (Ferrara et al, 2005; Kobashi et al, 2007; Matulis et al, 2008). The ability of IFN- γ -based tests to detect latent infection has been more difficult to study due to the lack of a gold standard diagnostic test; however, several TB outbreak studies have demonstrated that the tests correlated better than the tuberculin skin test with the degree of exposure that contacts had to the index TB case (Brock et al, 2004; Ewer et al, 2003). In addition, TB contact tracing studies have shown that patients who had a positive QuantiFERON-TB Gold test result and were not treated for latent TB infection were much more likely to develop active TB during longitudinal follow-up than those who had a positive tuberculin skin test and a negative QuantiFERON-TB Gold test result (Higuchi et al, 2007; Diel et al, 2008).

Although the performance of the new IFN- γ -based blood tests for active or latent *M. tuberculosis* infection have not been well validated in the immunosuppressed population, experts believe these new tests will be at least as, if not more, sensitive, and definitely more specific, than the tuberculin skin test (Barnes, 2004; personal communication, April, 2008 TB Advisory Board).

Performing the QuantiFERON-TB Gold In Tube Test

The QuantiFERON-TB Gold test In-Tube format will be provided for this study. The In-Tube format contains 1 additional *M. tuberculosis*-specific antigen, TB7.7 (p4), which is thought to increase the specificity of the test.

To perform the test using the In-Tube format, blood is drawn through standard venipuncture into supplied tubes that already contain the *M. tuberculosis*-specific antigens. Approximately 3 tubes will be needed per subject, each requiring 1 mL of blood. One tube contains the *M. tuberculosis*-specific antigens, while the remaining tubes contain positive and negative control reagents.

APPENDIX B TUBERCULIN SKIN TESTING

Administering the Mantoux Tuberculin Skin Test

The Mantoux tuberculin skin test (CDC, 2000) is the standard method of identifying persons infected with *Mycobacterium tuberculosis*. Multiple puncture tests (Tine and Heaf) should not be used to determine whether a person is infected because the amount of tuberculin injected intradermally cannot be precisely controlled. Tuberculin skin testing is both safe and reliable throughout the course of pregnancy. The Mantoux tuberculin test is performed by placing an intradermal injection of 0.1 mL of tuberculin into the inner surface of the forearm. The test must be performed with tuberculin that has at least the same strength as either 5 tuberculin units (TU) of standard purified protein derivative (PPD) S or 2 TU of PPD RT 23, Statens Seruminstitut, as recommended by the World Health Organization. PPD strengths of 1 TU or 250 TU are not acceptable (Menzies, 2000). Using a disposable tuberculin syringe with the needle bevel facing upward, the injection should be made just beneath the surface of the skin. This should produce a discrete, pale elevation of the skin (a wheal) 6 mm to 10 mm in diameter. To prevent needle-stick injuries, needles should not be recapped, purposely bent or broken, removed from disposable syringes, or otherwise manipulated by hand. After they are used, disposable needles and syringes should be placed in puncture-resistant containers for disposal. Institutional guidelines regarding universal precautions for infection control (eg, the use of gloves) should be followed. A trained health care worker, preferably the investigator, should read the reaction to the Mantoux test 48 to 72 hours after the injection. Subjects should never be allowed to read their own tuberculin skin test results. If a subject fails to show up for the scheduled reading, a positive reaction may still be measurable up to 1 week after testing. However, if a subject who fails to return within 72 hours has a negative test, tuberculin testing should be repeated. The area of induration (palpable raised hardened area) around the site of injection is the reaction to tuberculin. For standardization, the diameter of the induration should be measured transversely (perpendicular) to the long axis of the forearm. Erythema (redness) should not be measured. All reactions should be recorded in millimeters, even those classified as negative.

Interpreting the Tuberculin Skin Test Results

In the US and many other countries, the most conservative definition of positivity for the tuberculin skin test is reserved for immunocompromised patients, and this definition is to be applied in this study to maximize the likelihood of detecting latent TB, even though the subjects may not be immunocompromised at baseline.

In the US and Canada, an induration of 5 mm or greater in response to the intradermal tuberculin skin test is considered to be a positive result and evidence for either latent or active TB.

In countries outside the US and Canada, country-specific guidelines for immunocompromised patients should be consulted for the interpretation of tuberculin skin test results. If no local country guidelines for immunocompromised patients exist, US guidelines must be followed.

Treatment of Latent Tuberculosis

Local country guidelines for immunocompromised patients should be consulted for acceptable antituberculous treatment regimens for latent TB. If no local country guidelines for immunocompromised patients exist, US guidelines must be followed.

References

Centers for Disease Control and Prevention. Core curriculum on tuberculosis: What the clinician should know (Fourth Edition). Atlanta, GA: Department of Health and Human Services; Centers for Disease Control and Prevention; National Center for HIV, STD, and TB Prevention; Division of Tuberculosis Elimination; 2000:25-86.

Menzies RI. Tuberculin skin testing. In: Reichman LB, Hershfield ES (eds). Tuberculosis, a comprehensive international approach. 2nd ed. New York, NY: Marcel Dekker, Inc; 2000:279-322.

APPENDIX C GUIDELINES FOR MTX DOSE ADJUSTMENTS FOR MTX-TOXICITY

- The following algorithm will be used to make the dose adjustments in the event of MTX-induced toxicities (see Section 8.1.2):

1. Mild toxicity

- *Labs*: liver function test results (AST or ALT) < 2 x upper normal limit (ULN) central laboratory, leukocyte count $\geq 3.5 \times 10^9$ cells per liter
- *Symptoms*: mild nausea, mild abdominal distress, and occasional mild headaches, no rash, and no oral ulceration
- *Adjustment*: confirm relevant laboratory findings and continue with the current dosing algorithm

2. Moderate toxicity

- *Labs*: liver function test results (AST or ALT) ≥ 2 x ULN but < 3 x ULN and a leukocyte count of $\geq 2.0 \times 10^9$ cells per liter but < 3.5×10^9 cells per liter
- *Symptoms*: moderate nausea, moderate abdominal distress, minimal macular erythematous rash, and minor oral ulceration
- *Adjustment*: confirm the laboratory findings, decrease the dose of MTX by 50%, and repeat the laboratory tests 2 weeks following the dose reduction
- If the liver function tests return to < 2 x ULN, and the leukocyte count returns to values between normal and 3.5×10^9 cells per liter, and nausea or headaches improve and rash and oral ulceration resolve, the MTX dose may be increased to the baseline dose at the investigator's discretion.
- If the liver function tests remain elevated (≥ 2 x ULN and < 3 x ULN) or the leukocyte count remains $\geq 2.0 \times 10^9$ cells per liter but < 3.5×10^9 cells per liter, or the nausea does not improve, the MTX dose should be decreased again by 50%.

3. Severe toxicity

- *Labs*: liver function tests results (AST and/or ALT) ≥ 3 x ULN, and the leukocyte count is < 2.0×10^9 cells per liter
- *Symptoms*: severe nausea and vomiting, severe abdominal pain, severe headaches, and diffuse rash or major oral ulceration
- *Adjustment*: confirm the laboratory findings and withhold MTX therapy for 2 weeks, then repeat laboratory tests
- If, after 2 weeks, the repeat liver function test results are between ULN and < 3 x ULN, the leukocyte count is $\geq 2.0 \times 10^9$ cells per liter, and nausea or headaches or rash and oral ulceration have improved, MTX can be restarted at 50% of the baseline dose, at the investigator's discretion.

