6.4 DMARD/Oral Corticosteroid Initiation/Adjustment

Subjects may adjust or initiate DMARDs and/or oral corticosteroids at the investigator's discretion. Permitted DMARDs include methotrexate (MTX), sulfasalazine (SSZ), hydrochloroquine (HCQ), chloroquine (CQ), and bucillamine.

Prohibited medications listed in Section 8.2 may not be initiated by subjects as long as they are receiving study agent administrations.

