8.1.2 Disease Modifying Antirheumatic Drugs/Systemic Immunosuppressives

Acceptable non-biologic DMARDs are MTX, SSZ, HCQ, chloroquine (CQ) or bucillamine.

DMARDs may be initiated or adjusted at the investigator's discretion.

Guidelines for MTX dose adjustment in the event of suspected MTX toxicity are provided in [Appendix C](#). The dose of MTX should be decreased 50% and/or a folic acid product should be started or increased in dose if AST/ALT increases ≥ 2 to < 3 times ULN during treatment. The MTX dose may be increased back to the baseline dose if the AST/ALT decreases to < 2 times ULN. The dose of MTX should be temporarily interrupted and a folic acid product should be started or increased in dose if AST/ALT increases to ≥ 3 times ULN and total bilirubin level is < 2 times ULN. See Section [10.3](#) for drug induced liver injury criteria that require permanent discontinuation of study agent administration.

All subjects using MTX at doses of ≥ 0.2 mg/kg weekly or who are at high risk of adverse reactions (eg, elderly age, renal impairment, chronic high-dose NSAIDs) should receive at least 5 mg oral folic acid or oral folinic acid weekly. Folic acid or folinic acid may also be initiated or increased for subjects using MTX for management of adverse events such as stomatitis, increased ALT/AST, leucopenia, or macrocytic anemia.

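### Section 8.1.2 permits methotrexate to return to baseline dose on AST/ALT alone where Appendix C directs a further 50% cut, and neither says which governs

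*Protocol*

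**What the plan says.** Section 8.1.2 (DMARDs/systemic immunosuppressives) first points elsewhere: "Guidelines for MTX dose adjustment in the event of suspected MTX toxicity are provided in" Appendix C. It then gives its own rule for AST/ALT of 2 to < 3x ULN: "The dose of MTX should be decreased 50% and/or a folic acid product should be started or increased in dose". For recovery it says: "The MTX dose may be increased back to the baseline dose if the AST/ALT decreases to < 2 times ULN". That rule sets no leukocyte or symptom condition and no time point.

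Appendix C opens with "The following algorithm will be used to make the dose adjustments in the event of MTX-induced toxicities" and refers back to Section 8.1.2. Its moderate tier joins two laboratory findings with *and*: AST or ALT 2 to < 3x ULN, and leukocytes 2.0 to < 3.5 x 10^9/L. Symptoms are listed separately. The first step is to confirm the laboratory findings, "decrease the dose of MTX by 50%, and repeat the laboratory tests 2 weeks following the dose reduction". Return to baseline dose is then allowed, at the investigator's discretion, only if liver tests are below 2x ULN, leukocytes have recovered, nausea or headaches have improved, and rash and oral ulceration have resolved. If liver tests or leukocytes stay in the moderate range, "or the nausea does not improve, the MTX dose should be decreased again by 50" percent.

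Two other places direct sites to these rules. Section 9.8 (hepatobiliary abnormalities) cites only Section 8.1.2 for MTX dose adjustment. Section 15 lists the Appendix C guidelines among the materials given to investigators. Section 6.4 adds that "Subjects may adjust or initiate DMARDs and/or oral corticosteroids" at the investigator's discretion, and MTX is among the permitted DMARDs.

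**The concern.** The conflict is at the step after the first response to toxicity, so rewording how a subject enters a tier would not remove it. Once AST/ALT has fallen below 2x ULN, an investigator working from Section 8.1.2 may restore the full dose. Appendix C joins its failure conditions with *or*, so recovered AST/ALT does not prevent the second cut when leukocytes are still low or nausea has not improved. What one text permits, the other directs against.

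The first step shows a smaller version of the same problem. The and/or in Section 8.1.2 is satisfied by folic acid alone, while Appendix C calls for the 50% cut and does not mention folic acid.

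At stake is subject safety: two sites can manage the same findings in opposite directions, each with protocol text to cite. The route is realistic, because a site handling a liver abnormality is sent by Section 9.8 to Section 8.1.2 and not to Appendix C.

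**Working it through.** The protocol gives no figure to reproduce here. The check sets the two recovery rules side by side and does the dose arithmetic.

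**Step 1: conditions.**

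| | Section 8.1.2 | Appendix C, moderate tier |
|---|---|---|
| Laboratory trigger | AST/ALT 2 to < 3x ULN | AST/ALT 2 to < 3x ULN *and* leukocytes 2.0 to < 3.5 x 10^9/L |
| First step | 50% cut and/or folic acid | 50% cut |
| Re-check | no time stated | laboratory tests 2 weeks after the cut |
| Return to baseline dose (*may*) | AST/ALT < 2x ULN | AST/ALT < 2x ULN, and leukocytes, nausea or headaches, rash and ulceration all recovered |
| Second cut (*should*) | none | AST/ALT, *or* leukocytes, *or* nausea not recovered |

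**Step 2: dose, as a percentage of baseline.**
- After the first cut: 100% x 0.5 = 50%.
- After the second cut, reading the further 50% as half of the current dose: 50% x 0.5 = 25%.
- Permitted by Section 8.1.2 once AST/ALT is < 2x ULN: up to 100%. Ratio 100/25 = 4.
- If only folic acid was given at the first step, the dose is still 100% and one cut gives 100% x 0.5 = 50%. Ratio 100/50 = 2.

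**Step 3: example.** A subject enters with both laboratory abnormalities and has the 50% cut. At the 2-week re-check AST/ALT is 1.5x ULN and leukocytes are 3.0 x 10^9/L. Section 8.1.2 permits up to 100%; Appendix C directs 25%.

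**Step 4: how often the rules part, as logic.** Take four yes/no findings at the re-check: AST/ALT < 2x ULN, leukocytes recovered, nausea improved, rash and ulceration resolved. That gives 2^4 = 16 combinations, and AST/ALT is < 2x ULN in 8 of them.
- In 6 of the 8 (leukocytes still low, nausea not improved, or both) Section 8.1.2 permits 100% and Appendix C directs 25%.
- In 1 of the 8 (everything recovered) both permit 100%.
- In 1 of the 8 (only rash or ulceration unresolved) Appendix C neither permits the return nor directs a cut.

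These are combinations of conditions, not expected numbers of subjects. The documents give no frequencies.

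**The case against.** The strongest reply is that both texts can be obeyed. Section 8.1.2 only permits the increase, so an investigator who follows Appendix C breaches neither. Section 8.1.2 also points to Appendix C just before its own AST/ALT rule, and can be read as a summary of the liver part with the full rule in the appendix. This stands as far as it goes, but no text states that order. An investigator who uses the permission in Section 8.1.2 complies with it while acting against Appendix C, and Section 9.8 gives only the former.

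The second reply is that few subjects are affected. As written, the moderate laboratory criterion needs both abnormalities, and leukocytes can only remain low if they were low at entry. A subject with raised AST/ALT alone does not meet it, and the protocol does not say whether symptoms alone place a subject in the tier. This stands and limits the scope. It limits the first-step difference in the same way, and Appendix C's silence on folic acid does not forbid it.

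A reader might go further and infer three things that the documents do not support.
- *That a subject is assigned 100% or ordered down to 25%.* The verbs are *may* and *should*.
- *That the conflict distorts the liver, neutrophil or efficacy results.* Background DMARDs may be started or adjusted at the investigator's discretion (Sections 6.4, 8.1 and 8.1.2), so MTX dose varies by design. Section 11 plans descriptive summaries of groups not randomly assigned in this study, with no hypothesis test. Nor does Section 3.2.6 make the leukocyte example likely: it speaks of neutrophils and platelets under IL-6 inhibition, whereas Appendix C concerns total leukocytes in toxicity caused by MTX.
- *That a baseline dose does not exist for subjects who started MTX in this study.* The term is undefined. It could mean the dose before the reduction. It could also be read through Section 11.2, which takes baseline for analysis from the primary study; that reading gives no value to later starters.

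**Conclusion.** The two texts conflict on the recovery step, and differ on the first step, for subjects managed as moderate MTX toxicity. With AST/ALT back below 2x ULN and leukocytes still 2.0 to < 3.5 x 10^9/L, or nausea not improved, Section 8.1.2 permits up to 100% of baseline dose where Appendix C directs 25%.

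The four-fold gap rests on three assumptions: the first 50% cut was made, the second cut is half of the current dose, and the permission in Section 8.1.2 is used at the Appendix C re-check. If folic acid alone was given first, the gap is two-fold. The leukocyte case also needs both laboratory abnormalities at entry.

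The point rests on subject safety and consistency between sites. It does not show which rule is right, and no planned estimate, test or sample size depends on it.

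**What to change.** Reconcile Section 8.1.2 and Appendix C on two matters: the conditions for returning to baseline dose or reducing again, and whether folic acid without a cut is an acceptable first step. State the full rule in one place, replace the text in the other with a reference to it, and point Section 9.8 to the same place. Say what baseline dose means for subjects who started or changed MTX under Section 6.4. Which rule applies is for the sponsor's medical team.

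The cost is a few sentences in an amendment or a clarification letter to sites, with no new data or procedures.

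### Protocol Appendix C and Section 8.1.2 give inconsistent methotrexate-adjustment rules for the same laboratory values

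*Protocol*

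**What the plan says.** Section 8.1.2 introduces Appendix C as the place where MTX toxicity is handled: "Guidelines for MTX dose adjustment in the event of suspected MTX toxicity are provided in" that appendix. Appendix C refers back to Section 8.1.2 and is directive: "The following algorithm will be used to make the dose adjustments in the event of MTX-induced toxicities".

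**Appendix C, laboratory lines**
- Mild: "liver function test results (AST or ALT) < 2 x upper normal limit (ULN) central laboratory, leukocyte count" at least 3.5 x 10^9/L. Dosing continues unchanged after the findings are confirmed.
- Moderate: AST or ALT at least 2 but below 3 "x ULN and a leukocyte count of" 2.0 to below 3.5 x 10^9/L. MTX is halved and the tests are repeated after 2 weeks.
- Severe: AST and/or ALT at least 3 "x ULN, and the leukocyte count is" below 2.0 x 10^9/L. MTX is withheld for 2 weeks.
- The moderate follow-up rule joins its findings differently. A second halving applies if the liver tests stay raised "or the leukocyte count remains" in the moderate range, or if nausea does not improve.

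**Section 8.1.2**
- For the lower band (2 to below 3 x ULN), the rule begins: "The dose of MTX should be decreased 50% and/or a folic acid product should be started or increased in dose if AST/ALT increases".
- For the upper band (3 x ULN or more, with total bilirubin below 2 x ULN), the rule begins: "The dose of MTX should be temporarily interrupted and a folic acid product should be started or increased in dose if AST/ALT increases to".
- Neither trigger has a leukocyte condition. Leucopenia appears only as one reason why folic or folinic acid may be started or increased.
- For liver-injury criteria that stop study agent, the section points to Section 10.3.

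**The concern.** Two passages that cite each other set different triggers for changing the same background drug. Sites are sent to both. Section 9.8 refers to Section 8.1.2 for MTX adjustment after a hepatobiliary abnormality, while Section 15 lists Appendix C among the materials given to investigators. No passage says which governs.

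The situation is foreseeable. MTX is permitted and may be started or adjusted during the study (Section 6.4), and Section 3.2.6 expects IL-6 inhibition both to lower neutrophils and to raise liver enzymes. Hepatobiliary parameters belong to the major secondary endpoint (Section 9.2.3) and are summarised by toxicity grade over time (Section 11.2.2). What is at stake is mainly consistent handling of subjects with the same laboratory values.

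**Working it through.** No sample size, power or alpha figure is involved, so the check is an enumeration followed by a side-by-side reading.

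**Step 1. Grid under the literal 'and'.** Inputs are the cut-points in Appendix C (AST/ALT at 2 and 3 x ULN; leukocytes at 3.5 and 2.0 x 10^9/L) and the Section 8.1.2 triggers. Both enzymes are taken to lie in the same band and bilirubin to be below 2 x ULN.

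| AST/ALT (x ULN) | Leukocytes (x 10^9/L) | Appendix C tier | Section 8.1.2 MTX trigger |
|---|---|---|---|
| < 2 | >= 3.5 | Mild | none |
| < 2 | 2.0 to < 3.5 | none | none |
| < 2 | < 2.0 | none | none |
| 2 to < 3 | >= 3.5 | none | halve and/or folic acid |
| 2 to < 3 | 2.0 to < 3.5 | Moderate | halve and/or folic acid |
| 2 to < 3 | < 2.0 | none | halve and/or folic acid |
| >= 3 | >= 3.5 | none | interrupt, plus folic acid |
| >= 3 | 2.0 to < 3.5 | none | interrupt, plus folic acid |
| >= 3 | < 2.0 | Severe | interrupt, plus folic acid |

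Three cells have a tier, so 9 - 3 = 6 do not. In 4 of those 6, Section 8.1.2 triggers MTX action. In the other 2 (isolated low leukocytes), neither passage has an MTX dose trigger.

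**Step 2. One enzyme raised.** Take ALT 2.5 x ULN, AST 1.0 x ULN and leukocytes 6.0 x 10^9/L. The mild line asks for AST *or* ALT below 2 x ULN. AST satisfies this, and 6.0 >= 3.5, so the mild laboratory line is met and dosing continues. Under Section 8.1.2, ALT lies between 2 and 3 x ULN, so halving and/or folic acid applies. Here the two passages give opposing instructions.

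**Step 3. The 'or' reading.** Suppose the worse of the two findings sets the tier: severe if AST/ALT >= 3 x ULN or leukocytes < 2.0; otherwise moderate if AST/ALT >= 2 x ULN or leukocytes < 3.5; otherwise mild. Then 0 of 9 cells are empty. The passages still do not agree. With AST/ALT below 2 x ULN and leukocytes at 2.0 to < 3.5 or < 2.0, Appendix C would be moderate or severe and Section 8.1.2 would have no dose trigger. With AST/ALT at 2 to < 3 x ULN and leukocytes < 2.0, Appendix C would be severe (withhold) and Section 8.1.2 would halve and/or add folic acid. That is 3 of 9 cells in disagreement.

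**Step 4. Actions and recovery.**
- Folic acid: an alternative or addition to halving in Section 8.1.2, and required with interruption. The Appendix C tiers do not mention it in the text available.
- Return to baseline dose after a moderate finding: AST/ALT below 2 x ULN is enough in Section 8.1.2. Appendix C also needs leukocyte recovery and symptom improvement.
- Bilirubin: a condition in Section 8.1.2 from 3 x ULN upward; absent from Appendix C.
- Cross-reference: the liver-injury criteria cited as Section 10.3 are in Section 10.2, item 9. Section 10.3 covers withdrawal from the study.

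**The case against.** The strongest reply is that these subjects are already looked after. Section 8.1.2 gives an MTX instruction for AST/ALT from 2 x ULN upward, subject to the bilirubin condition at 3 x ULN and above, and Section 9.8 routes hepatobiliary abnormalities to it. Study agent is interrupted at AST/ALT of 3 x ULN or more whatever the leukocyte count (Table 4), with confirmatory testing (Section 9.8) and permanent stopping criteria (Section 10.2, item 9). Low neutrophils have their own rule. This stands. A reader might infer that a subject with an isolated elevation is left without guidance, and the documents do not support that.

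A second reply is that the 'and' may only list findings. The moderate symptom line is also joined by 'and', and requiring every listed symptom together would be odd. The reading is plausible, but the protocol does not adopt it, and Step 3 shows that it leaves disagreements with Section 8.1.2.

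Third, a reader might infer that every isolated elevation of 2 x ULN or more falls outside all three tiers. It does not. With one enzyme raised the mild line can be met, and Appendix C does not say how its laboratory and symptom lines combine, so a symptomatic subject might be placed by symptoms. The gap is confined to laboratory placement with both enzymes raised.

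Fourth, it can be said that where Appendix C is silent, Section 8.1.2 simply stands. That answers the empty cells, but not the one-enzyme case, the folic acid difference or the recovery conditions.

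Finally, the available Appendix C text ends within the severe tier, and the contents list allows it to run to a further page. The laboratory entry criteria of all three tiers are visible.

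**Conclusion.** The inconsistency is real and lies between two current passages of the protocol. On the literal wording, 6 of 9 liver-by-leukocyte combinations have no Appendix C laboratory tier, and Section 8.1.2 triggers MTX action in 4 of them. One raised enzyme can lead to opposing instructions. The defect is conflicting MTX guidance, not absent guidance, and the study-agent safeguards operate independently of it.

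This rests on three assumptions: AST/ALT in Section 8.1.2 means either enzyme, the Appendix C conjunctions are read as written, and bilirubin is below 2 x ULN where interruption is shown.

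A reader might infer that the hepatobiliary summaries are distorted. The documents do not support a claim of that kind. The number of subjects affected cannot be computed, MTX may in any case be adjusted at the investigator's discretion, and the analyses are descriptive without hypothesis tests. No statistical figure changes. The point still merits correction, because it concerns contradictory instructions on subject safety and goes beyond a clerical slip.

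**What to change.** Reconcile Appendix C and Section 8.1.2 so that both carry the same trigger logic (including whether liver and leukocyte findings combine by 'and' or 'or', and whether one raised enzyme suffices), the same position on folic acid and bilirubin, and the same conditions for returning to the baseline dose. Alternatively, state which passage governs where they differ. Correct the pointer in Section 8.1.2 from Section 10.3 to Section 10.2, item 9. Which clinical rule is adopted is for the sponsor's medical team, and an exhaustive new algorithm is not needed.

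The cost is wording in one section and one appendix, carried into the copy of Appendix C supplied to investigators. No new procedure, assessment or analysis is required.
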